- to evaluate the safety of the proposed regimen of preventive therapy with Ingaron (INN: human recombinant interferon gamma, lyophilizate for the preparation of solution for intranasal administration of 100,000 IU) in adult volunteers. Safety is assessed based on adverse events, clinically significant changes in laboratory parameters during the study, taking into account the assessment of severity according to the STCAE 4.03 scale.

OBJECTIVES OF NON-INTERVENTIONAL RESEARCH

Primary objective

To evaluate the effectiveness of the prophylactic use of Ingaron (INN: human recombinant interferon gamma, lyophilizate for the preparation of solution for intranasal administration of 100,000 IU) in the mode of 3 drops in each nasal passage intranasally every other day for 10 days with break of 7 days (2 10-day cycles) in adult volunteers.

Secondary objectives

Safety assessment of the prophylactic use of Ingaron (INN: human recombinant interferon gamma; lyophilizate for the preparation of a solution for intranasal administration of 100,000 IU), applied 3 drops into each nasal passage intranasally every other day for 10 days with break of 7 days (two 10-day cycles) in adult volunteers.

Efficacy and safety include evaluation based on epidemiological, anamnestic, and clinical data, as well as laboratory studies and specialized scales.

DESIGN OF A NON-INTERVENTIONAL STUDY

Post-marketing prospective randomized open-label comparative non-interventional study in parallel groups.

A total of 4 visits are planned (0–3). Visit 0 and 1 can be combined.

Main stages of the study

1. Visit 0. Conducted in person⁷. Screening: informed consent, inclusion of volunteers and distribution into groups (Day -3-1)
2. Visit 1. Conducted in person. Randomization. Delivery of the investigated drug and the diary of the researcher participant (Day 0)
3. Visit 2. It is carried out remotely (by phone). Completion of a preventive course, evaluation of preventive efficacy and safety during the period of drug administration. The beginning of the observation period. (Day 28–30)
4. Visit 3. Conducted in person. Completion of the observation and research period. (Day 56–62)

The main procedures and stages of the study are reflected in the Schedule of research procedures.

The total duration of participation is about 2 months (56–62 days).

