- presence of a direct temporary connection of AE with specific administration of the drug (for example, development of AE during instillation);
- possibility of explaining the development of AE by the pharmacological effect of the drug;
- availability of information about such AE as a possible side effect in Clinical Investigation Brochure/guidelines for medical use;
- description of similar cases in the literature;
- presence of additional specific data indicating the association of AE with the drug (for example, the presence of specific antibodies, positive result of allergological tests);
- positive test with the withdrawal of the study drug (AE was resolved or its severity decreased after the drug was discontinued);
- positive test with repeated administration of the drug under study (AE reappeared or its severity worsened with repeated administration of the drug after withdrawal);
- presence of other reasons for the development of this AE (manifestations of the underlying disease, concomitant diseases and conditions, concomitant therapy, food, lifestyle, etc.).

The association of adverse events with the study drug will be evaluated based on the following principles in accordance with the WHO classification:

- **reliable** – clinical manifestations, including violations of laboratory parameters that occur during the period of taking drug s and which cannot be explained by the presence of existing diseases and the influence of other factors and chemical compounds. Manifestations of an adverse reaction regress after the drug is discontinued and occur when it is re-prescribed;
- **probable** – clinical manifestations, including changes in laboratory parameters associated with the instillation of the drug, which are unlikely to be related to concomitant diseases or other factors and which regress with the withdrawal of the drug. The response to the rechallenge is unknown;
- **possible** – clinical manifestations, including changes in laboratory parameters associated with the use of the drug, but which can be explained by the presence of

¹¹ Due to statistical necessity, adverse events are recorded both in the study group and in the control group. Evaluation and registration of adverse events begins from the moment of signing the informed consent form.

concomitant diseases or taking other drugs and chemical compounds. Information about the reaction to drug withdrawal is unclear;

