Features of AE registration in some cases:

Lack of preventive effect

Absence of preventive effect of therapy should not be registered as AE.

Pregnancy

All cases of pregnancy that developed in the participants of the clinical trial against the background of the study therapy during the period of participation in the study are subject to mandatory registration in the Pregnancy Registration Form and are not accompanied by the registration of AE/SAE. The signed and dated pregnancy form is sent to LLC "NPP "Pharmaclon" by e-mail: [contact] , - within 5 working days from the date of notification of the research doctor.

AE in the period before taking study drug

In the presence of deviations of laboratory, physiological and/or instrumental indicators at the screening or randomization visit before the first use of the drug, in the future, the following are subject to registration as AE:

- all deviations accompanied by an increase in severity according to the version used;
- deviations that are not associated with a change in severity, but have, from the researcher's point of view, clinical significance.

If the participant had deviations of laboratory, physiological and/or instrumental indicators at the visit before the first use of the study drug, after which the indicators during the study normalized or the severity of the deviation changed for the better, and then changed again for the worse, but the values of the indicators remained within the same severity according to If the patient was on a visit before the first use of the study drug, the phenomenon should not be registered as AE, except in cases where it is clinically significant from the point of view of the research physician.

Registration of a disease/syndrome characterized by several symptoms

In case of registration of a disease accompanied by various symptoms, registration of individual symptoms as AE is not required, however, it is recommended to list all the symptoms of the disease in the note to the description of the AE.

For more detailed information on the procedures for registration and evaluation of adverse events under this Protocol, see the Guide on Adverse Events Version 2 of 17/02/2021.

QUALITY CONTROL

Direct access to primary data/documentation

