4. Open the vial of water for injection by breaking off its upper part.
5. Pour 5 ml of water for injection into glass vial with a dry substance.
6. Remove the dropper cap from the package and fix it on the neck of the bottle.

Due to the need to store the active substance in a full vacuum, the aluminum cap must be hermetic and durable. Slowly remove the aluminum guard of the bottle, avoid cuts. If the cap breaks off during removal, you can remove the rest of the metal cap with scissors.

Take vial with Ingaron with liquid inside with both hands and turn it over 10–15 times.

Put the vial with Ingaron with the liquid inside in the refrigerator and store there for 10 days. For the second course of prevention (after 1 week), use the second vial.

Return the empty ampoules of water for injection together with the used glass vials to the researcher at the next visit.

Administration

Course 1. The drug is applied 3 drops in each nasal passage every other day 30 minutes before breakfast for 10 days (total of 5 instillations). The use of the drug is carried out according to the following regimen:

- Course 1. Day 1 – mark administration time in your diary
- Course 1. Day 3 – mark administration time in your diary
- Course 1. Day 5 – mark administration time in your diary
- Course 1. Day 7 – mark administration time in your diary
- Course 1. Day 9 – mark administration time in your diary

This is 1 preventive cycle. Then a break of 7 days.

Course 2. Drug administration is carried out similarly to Course 1. Preparation of the drug is carried out similarly to the algorithm described earlier. Dosage regimen is the same:

- Course 2. Day 1 – mark administration time in your diary
- Course 2. Day 3 – mark administration time in your diary
- Course 2. Day 5 – mark administration time in your diary
- Course 2. Day 7 – mark administration time in your diary
- Course 2. Day 9 – mark administration time in your diary

If you missed drug administration, mark the day in your diary with a "check mark" and take the next dose the next morning 30 minutes before breakfast and then continue using it every other day. Remember that the finished solution of the drug is stored for no more than 10 days in the refrigerator. Do not use it after the expiration date. For Course 2, use the second bottle, do not use the first bottle, even if the drug is not fully used.

| | |
|---------------------------------|---|
| Course 1 Day 1 | Date ____ ____ ____ ____ ____ ____ day month year |

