4.2. Registration, analysis, and evaluation of safety parameters

Adverse events were recorded from the moment of signing the informed consent until the end of the study. The safety analysis of the drug will consider the data of physical examination, diaries of participants, laboratory tests or other assessments. The study will analyze the frequency of occurrence and the nature of AE and SAE. The safety assessment was carried out throughout the study.

Adverse event (AE)

Adverse event (AE) – any adverse change in the state of health of the patient or the subject of a clinical trial to whom the drug (study) product was prescribed, regardless of the causal relationship with its use. AE may represent any adverse and unintended change (including deviation of the laboratory indicator from the norm), symptom or disease, the time of occurrence of which does not exclude a causal relationship with the use of drug product, regardless of the presence or absence of a relationship with the use of drug product¹.

Symptoms of acute respiratory infection: fever, manifestations of general infectious intoxication, signs of respiratory damage are not considered as adverse event, however, they are recorded during the study and analyzed as data for evaluating effectiveness.

Adverse reaction (AR)

Adverse reaction (AR) – an unintentional adverse reaction of the body associated with the use of a drug and suggesting the presence, at least, of a possible relationship with the use of a suspected medicinal product.

Determination of a serious adverse event (SAE)

Serious adverse event (SAE) – AE that leads to death², poses a threat to life³, requires hospitalization of the patient or its prolongation⁴, leads to persistent or severe uncapacity or disability, to congenital anomalies or malformations⁵, requires medical intervention to prevent the development of these conditions.

¹ Due to statistical necessity, adverse events are recorded both in the study group and in the control group. Evaluation and registration of adverse events begins from the moment of signing the informed consent form.

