Visit	Group	Parameter	SBP (mmHg)	DBP (mmHg)	HR (beats/min)	RR (/min)	Temperature (°C)	Oxygenation (SpO ₂)
		min.						
		max.						
		Me						
	p (between groups)							
	B3	N						
		M						
	GROUP I	CO						
		min.						
		max.						
		Me						
	GROUP II	N						
		M						
		CO						
		min.						
		max.						
		Me						
p (between groups)								

Table 18. Total number of AE, SAE in groups (safety population)

Group	AE	SAE
GROUP I	n/N (%)	n/N (%)
GROUP II	n/N (%)	n/N (%)
p (between groups)		

Table 19. Number of subjects with reported adverse events (safety population)

Group	AE+	AE-
GROUP I	n/N (%)	n/N (%)
GROUP II	n/N (%)	n/N (%)
p (between groups)		

Table 20. Adverse events that developed in the study group participants (safety population)

N	Mild AE		Moderate AE		Severe AE		Total		Total
	Organ system / AE	C	HC	C	HC	C	HC	C	HC
Organ system x	n/N (%)								
AE x	NN1 NN2 NNX								

Note: the table shows all the AE that chronologically occurred in the group after at least one use of the study drug.

C – related to the study drug

HC – not related to the drug under study

NNx – participant's number with the corresponding AE

Table 21. Adverse events that have developed in the subjects of the control group (safety population)

N	Mild AE	Moderate AE	Severe AE	Total

Organ system / AE	C	HC	C	HC	C	HC	C + HC
Organ system x	n/N (%)						
AE x	NN1 NN2 NNX						

Note: The table shows all AE that occurred in the control group at any time after randomization into the study.

NNx – participant's number with the corresponding AE

Table 22. Adverse events by nosology (safety population)

SOC	PT	Group 1	Group X
Category SOC 1	Category PT 1	n/N (%)	n/N (%)
	Category PT x	n/N (%)	n/N (%)
Category SOC x	Category PT 1	n/N (%)	n/N (%)
	Category PT x	n/N (%)	n/N (%)

Table 23. Severity of AE (safety population)

Group	Mild	Moderate	Severe
GROUP I	n/N (%)	n/N (%)	n/N (%)
GROUP II	n/N (%)	n/N (%)	n/N (%)

Table 24. Results of comparison of groups by vaccination status against COVID-19 (ITT/PP/ITT_NV/PP_NV/ITT_NV_BE/PP_NV_BE population)

	GROUP I	GROUP II
Total subjects	N	N
Not vaccinated	n/N (%)	n/N (%)
Vaccinated	n/N (%)	n/N (%)
p (between groups)

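### Adverse events are listed from first drug use in Group I but from randomisation in Group II, and the side-by-side AE tables state no window; one common start is needed

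*SAP*

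**What the plan says.** **Listings by group (SAP section 6).** The note to Table 20, for the study group, shows "all the AE that chronologically occurred in the group after at least one use of the study drug". The note to Table 21, for the control group, shows "all AE that occurred in the control group at any time after randomization into the study". Both shells give n/N (%) by organ system, and neither has a row for a between-group p value.

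**Side-by-side tables (SAP section 6).** Tables 18 and 19 compare the groups on AE and SAE totals and on subjects with an event, each with a p row. Tables 22 and 23 set the groups side by side by nosology and severity, without a p row. None of the four states an AE window.

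**Recording.** SAP 4.2 says: "Adverse events were recorded from the moment of signing the informed consent until the end of the study". Protocol footnote 11, in the section on causal relationship, says: "Due to statistical necessity, adverse events are recorded both in the study group and in the control group", and it also starts registration at consent. No difference by group is made.

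**Timing of first use.** The Protocol's list of study stages places randomisation and drug hand-out at Visit 1, Day 0. The diary instructions in Appendix 1 say: "The drug is applied 3 drops in each nasal passage every other day 30 minutes before breakfast for 10 days". No maximum delay between randomisation and first use is stated.

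**The concern.** Safety of the prophylactic regimen is the Protocol's secondary objective. SAP 4.1 names AE and SAE frequency, overall and by organ system, as the first safety variable. Tables 20 and 21 are the paired listings a reader will lay next to each other for that purpose, yet their start points differ by group and no reason is given. An event between randomisation and first use is left out of the Group I listing, while an event at the same point in follow-up stays in the Group II listing.

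A second consequence is internal. The only AE windows written in the table shells are these two unequal ones. Whoever programs Tables 18, 19, 22 and 23 could count from consent, from randomisation, or with the two unequal rules, and the SAP does not decide. Depending on that choice, the totals in Tables 18 and 19 need not match those in Tables 20 and 21. In an open-label trial, an unexplained rule that can move the count in only one direction invites criticism that is easily avoided.

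**Working it through.** There is no stated figure to reproduce, since the plan's sample size, power and alpha do not enter this point. The check sets the windows side by side and then sizes the mismatch.

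**1. Windows**

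| Place | Group I starts at | Group II starts at |
|---|---|---|
| Recording (SAP 4.2; Protocol footnote 11) | consent | consent |
| Listings (Tables 20 and 21) | first use | randomisation |
| Side-by-side tables (18, 19, 22, 23) | not stated | not stated |

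Recording runs to the end of the study in both groups, so nothing at the far end offsets the later start in Group I.

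**2. Range for the gap g (days from randomisation to first use).** From the diary, course 2 starts 17 days after course 1 (10 + 7), and its last instillation is 8 days after that. With first use on Day g, the last instillation falls on Day g + 25. Visit 2 closes the preventive course and takes place at the latest on Day 30 (27 + 3 in the schedule table; 28–30 in the list of stages).

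- g = 1: Day 26
- g = 3: Day 28
- g = 5: Day 30, the last that fits
- g = 7: Day 32, which does not fit

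Gaps of 1 and 3 days are used below. Both are assumptions.

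**3. Share of follow-up lost in Group I = g/T**, with T = 56 to 62 days from the Protocol, at a constant AE rate that is equal in both groups.

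- g = 1: 1/56 = 1.79%; 1/62 = 1.61%. Apparent rate ratio 0.982 to 0.984.
- g = 3: 3/56 = 5.36%; 3/62 = 4.84%. Apparent rate ratio 0.946 to 0.952.

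**4. Share of subjects with an AE.** With control proportion p (assumed) and T = 56, the Group I proportion under no true difference is p1 = 1 − (1 − p)^((T − g)/T).

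**5. Effect on a test, if the unequal windows were carried into Table 19.** This is hypothetical, because the SAP does not say so. With 315 per group (SAP 5.2), d = p − p1 and SE = √[(p(1 − p) + p1(1 − p1))/315], the two-sided rejection rate at 0.05 is Φ(d/SE − 1.96) + Φ(−d/SE − 1.96).

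| p | p1, g = 1 | drop (points) | rejection | p1, g = 3 | drop (points) | rejection |
|---|---|---|---|---|---|---|
| 5% | 4.91% | 0.09 | 5.0% | 4.74% | 0.26 | 5.3% |
| 10% | 9.83% | 0.17 | 5.1% | 9.49% | 0.51 | 5.5% |
| 20% | 19.68% | 0.32 | 5.1% | 19.04% | 0.96 | 6.1% |
| 40% | 39.45% | 0.55 | 5.2% | 38.34% | 1.67 | 7.1% |

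With a common start the mismatch is 0 days and the rejection rate stays at 5.0%.

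**The case against.** The best defence is that the restriction sits in one single-group listing that separates related from unrelated events. Limiting such a listing to events after exposure is a recognisable choice, and it fits the causality criterion, which looks at events after the start of drug use. The tables that set the groups side by side carry no such limit, recording starts at consent for everyone, and the gap is probably about a day.

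Much of this stands. The documents do not show that the planned between-group AE comparison uses unequal windows. What does not fall away is that the listings report frequencies for both groups, their stated windows differ by group without a reason, and the comparative tables leave the window open.

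Four stronger readings are tempting, and the documents do not support them:

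- **That AEs in the two groups cannot be compared.** Events are recorded with dates from consent in both groups, so a common window can be applied to the same data.
- **That first use could lag by a week, costing Group I more than a tenth of follow-up.** No explicit deadline exists, but a delay of that length puts the last instillation after the latest Visit 2 (step 2 of the working).
- **That the Table 20 note erases every event in Group I participants who never use the drug.** Their place is set by SAP 5.5. The safety set equals an ITT set defined by exposure and is analysed by actual treatment, so they are either outside the set or not counted as treated. Rewording the note would not change that. How that exposure wording applies to untreated controls is a separate question.
- **That the Protocol's rule for pre-existing deviations has no baseline in Group II.** The rule refers to findings "at the screening or randomization visit before the first use of the drug", and Group II attends both of those visits.

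**Conclusion.** The point holds as an inconsistency of small size and known direction. Tables 20 and 21 use different start points, Tables 18, 19, 22 and 23 use none that is stated, and recording uses a third. For Tables 20 and 21 the mismatch can only lower the Group I count. It is worth about 1.6 to 1.8% of follow-up at an assumed one-day gap and about 5% at three days, given a constant AE rate. Even if the unequal windows reached Table 19, a one-day gap would hardly move the error rate, and a three-day gap would take it to at most 7.1% over the AE proportions tried. This is a minor correction to the table shells. It is not evidence that the safety comparison is biased.

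**What to change.** State one AE window for Tables 18 to 23: from randomisation to the end of participation, in both groups. Reword the notes to Tables 20 and 21 to match, and add the same sentence to Tables 18, 19, 22 and 23. Put events between consent and randomisation in a separate listing for both groups. Keep the after-first-use list for Group I as a supplementary listing, labelled as such.

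The cost is two reworded notes, one repeated sentence and two simple listings. AE start dates are already required in the source records, so no new data are needed and study conduct does not change. The change should be made before the tables are programmed.
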